#### **8.4.8. Adverse Events of Special Interest**

The following events are considered AESIs:

- A confirmed diagnosis of myocarditis or pericarditis. See [Section 8.10.8](#) for additional procedures for monitoring of potential myocarditis or pericarditis.

AESIs are examined as part of routine safety data review procedures throughout the clinical trial and as part of signal detection processes. Should an aggregate analysis indicate that these prespecified events occur more frequently than expected, eg, based on epidemiological data, literature, or other data, then this will be submitted and reported in accordance with Pfizer's safety reporting requirements. Aggregate analyses of safety data will be performed on a regular basis per internal SOPs.

All AESIs must be reported as an AE or SAE following the procedures described in [Sections 8.4.1](#) through [8.4.4](#). An AESI is to be recorded as an AE or SAE on the CRF. In addition, an AESI that is also an SAE must be reported using the Vaccine SAE Reporting Form.

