#### **8.4.7. Disease-Related Events and/or Disease-Related Outcomes Not Qualifying as AEs or SAEs**

ILIs and their sequelae, including pneumonia and death, that are potentially consistent with any clinical efficacy endpoint definitions should not be recorded as AEs. These data will be captured as efficacy assessment data only on the relevant pages of the CRF, as these are expected endpoints.

ILIs and their sequelae will not be reported according to the standard process for expedited reporting of SAEs, even though the event may meet the definition of an SAE. These events will be recorded on the ILI visit pages in the participant's CRF within 1 day.

NOTE: However, if either of the following conditions applies, then the event must be recorded and reported as an SAE (instead of a disease-related event):

- The event is, in the investigator's opinion, of greater intensity, frequency, or duration than expected for the individual participant.

OR

- The investigator considers that there is a reasonable possibility that the event was related to study intervention.

ILIs and their sequelae will be reviewed by an internal blinded case reviewer. Any SAE that is determined by the internal case reviewer NOT to meet any clinical primary efficacy endpoint criteria is reported back to the investigator site of incidence. The investigator must report the SAE to Pfizer Safety within 24 hours of being made aware that the SAE did not meet endpoint criteria. The investigator's SAE awareness date is the date on which the investigator site of incidence receives the SAE back from the internal case reviewers.

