#### 8.10.6.1. ILI Visit (Within 5 Days After ILI Onset)

This visit may be conducted as an in-person (eg, at the study site, or in the participant's home (home health visit, see [Section 8.1.2](#)) or telehealth visit (see [Section 8.1.1](#)); a telehealth visit involves the sharing of healthcare information and services via appropriate telecommunication technologies (eg, audio, video, video-conferencing software) remotely, thus allowing the participant and investigator to communicate on aspects of clinical care.

As a participant's ILI may evolve over time, several contacts may be required to obtain the following information:

- If needed, provide self-swab kits and instructions on self-collection of midturbinate swabs.
- If the visit is conducted in person, obtain 2 midturbinate swabs (collected by site staff), 1 from each nostril. Alternatively, if conducted by telehealth, instruct the participant to self-collect 2 midturbinate swabs, 1 from each nostril, and ship to the central laboratory for assessment.
- Perform clinical assessment, including temperature and, if the ILI visit is being conducted in person, respiratory rate. Collect details of any ILI symptoms reported by the participant (if used, the participant may refer to the ILI memory aid to recall details of these symptoms) or noted via clinical assessment, including severity (see [Section 10.2.3](#)) and duration of

- CCI [REDACTED]
- [REDACTED]

- Following ILI symptom resolution, confirm, based on the participant's own assessment:
  - Has the participant returned to the same level of health as prior to the onset of ILI?
  - Is the participant able to conduct daily activities as prior to the onset of ILI?
  - Has the participant required nonprofessional (eg, family member) assistance for ILI?
- Collect ILI-related standard-of-care clinical and laboratory information. This includes, but is not limited to:
  - Number and type of any healthcare contact; duration of hospitalization and ICU stay; date of visit.
  - Mechanical ventilation use (if applicable).
  - Oxygen saturation.
  - Oxygen use (if applicable).
  - Local test results for influenza and any local noninfluenza respiratory pathogen testing, including the trade name of the testing platform used.
  - Results of x-rays or CT scans if performed.
  - Clinical diagnosis and sequelae, eg, pneumonia.
  - Concomitant medications used to treat ILI symptoms.
  - Death.
- Record nonstudy vaccinations as described in [Section 6.9](#).

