#### **8.10.8. Additional Procedures for Monitoring of Potential Myocarditis or Pericarditis**

Any study participant who reports acute chest pain, shortness of breath, palpitations, or any other symptom(s) that might be indicative of myocarditis or pericarditis within 14 days after the study intervention administration should be specifically evaluated for possible myocarditis or pericarditis.

In addition to a clinical evaluation, the following should be performed:

- ECG and
- Measurement of the troponin level

If myocarditis or pericarditis is suspected based upon the initial evaluation, the following should also be performed:

- Evaluation by a cardiologist,
- Cardiac echocardiogram, and/or
- Cardiac magnetic resonance study

Details of the symptoms reported, and results of the investigations performed, will be recorded in the CRF.

An evaluation is not required if, in the investigator's opinion, the symptoms reported are more indicative of ILI. In that case, the procedures described in [Section 8.10.6](#) should be performed.

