3.1.2.4. Adverse Events

Standard algorithms for handling missing AE dates and missing AE severity will be applied as described in the Pfizer vaccine data standard rules. AEs will be collected from the time the participant provides informed consent through 4 weeks following vaccination.

Any AE reported in the CRF and considered as a reactogenicity event ([Section 3.1.2](#)) during clinical review and the data pooling process will not be included in any of the derivation included in [Section 3.1.2.4](#) and Section 3.1.2.5. However, if those reactogenicity AEs lead to discontinuation, or are immediate AEs, SAEs, or medically attended AEs, they will still be included in the AE data.

The following derivations will be included for each participant:

- Any AE reported.
- Any related AE reported.
- Any immediate AE (assess acute reactions for at least 30 minutes after study intervention administration).
- Any severe AE.
- Any life-threatening AE.
- Any AE leading to study withdrawal.
- Any AE leading to death.
- Any AESI.
 - A confirmed diagnosis of myocarditis or pericarditis.

The following analysis intervals will be defined for the above endpoints:

- From Day 1 (vaccination day) through 7 days after vaccination.
- From Day 8 through 4 weeks after vaccination (Visit 3).
- From Day 1 through 4 weeks after vaccination (Visit 3).

The analysis interval of “From 4 weeks after vaccination (Visit 3) through 6 months after vaccination (Visit 4)” will also be defined for endpoints of ‘Any AE leading to death’ and ‘Any AESI’.

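### Protocol 8.4.7 and 8.4.8 give conflicting recording rules for a confirmed myocarditis or pericarditis regarded as an ILI sequela, so some cases may be missed from the SAP's count of confirmed AESIs

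*Protocol*

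**What the plan says.** **Protocol 8.4.8** names one AESI, confirmed myocarditis or pericarditis, with no limit by cause. "All AESIs must be reported as an AE or SAE", by the route of Sections 8.4.1 through 8.4.4, and "An AESI is to be recorded as an AE or SAE on the CRF". A serious AESI also goes on the Vaccine SAE Reporting Form.

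**Protocol 8.4.7** says that ILIs and their sequelae, with pneumonia and death named as examples, "that are potentially consistent with any clinical efficacy endpoint definitions should not be recorded as AEs". They are efficacy data, kept on the ILI visit pages and outside expedited SAE reporting. A NOTE lists two conditions under which the event must instead be recorded and reported as an SAE. One is: "The event is, in the investigator's opinion, of greater intensity, frequency, or duration than expected for the individual participant". The other is a reasonable possibility that study intervention caused it. A blinded internal reviewer sends back to the site any SAE that does not meet the primary efficacy endpoint criteria, and the site must then report it within 24 hours.

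**Protocol 8.4.1(a)** puts ILI-related deaths, pneumonia and hospitalizations on the ILI page and not on the AE or SAE route. **Protocol 8.10.6.1** repeats the 8.4.7 rule and has sites collect "Clinical diagnosis and sequelae, eg, pneumonia" at the ILI visit.

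**SAP 3.1.2.4** derives the AESI variable inside its adverse-event section, specified as "A confirmed diagnosis of myocarditis or pericarditis", with intervals that run to Visit 4. **SAP 6.1.3.2** reports AESIs as a supplementary AE summary. Separately, **Protocol 9.3.5** and **SAP 6.6.1** summarize or list cardiac test results or suggestive symptoms, but only within 14 days after vaccination.

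**The concern.** For a confirmed myocarditis that the investigator regards as a complication of influenza, one section requires an AE or SAE record and the section before it says not to make one. Neither refers to the other, so two sites could follow the protocol and file the same event in different places.

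The protocol itself foresees that the two pictures overlap. Section 8.10.8 sends a participant down the ILI pathway when, in the investigator's opinion, "the symptoms reported are more indicative of ILI".

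The SAP count is built on AE data, and nothing in it brings in diagnoses from the ILI page. This is the only AESI, and Protocol 2.3.1 lists it among the risks carried over from the BNT162b2 experience. Very few cases are expected, so the filing of one or two can decide whether a vaccine group shows any case at all.

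**Working it through.** **1. Is there a way out through the cross-reference?** Section 8.4.8 sends the site to 8.4.1 through 8.4.4 and not to 8.4.7. That would settle the matter if 8.4.1 were free of the carve-out. It is not: 8.4.1(a) keeps ILI-related hospitalizations and deaths off the AE and SAE route and points to 8.4.7. Section 8.10.6.1 repeats the rule at the visit where the diagnosis would be collected. None of the three mentions AESIs.

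**2. Which cases are exposed?** Take a confirmed myocarditis or pericarditis regarded as an ILI sequela, and suppose the site follows 8.4.7 and finds neither NOTE condition met. The reviewer route covers SAEs only, and the primary endpoint needs symptom onset from 14 days after vaccination (Protocol 9.1.1), which is Day 15 (SAP 3.1.1.2).

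| Case | Returned by the reviewer? | Result |
|---|---|---|
| Serious, ILI onset before Day 15 | Yes, cannot meet the primary endpoint | Reported as an SAE |
| Serious, onset from Day 15, influenza not confirmed | Yes | Reported as an SAE |
| Serious, onset from Day 15, primary-endpoint LCI | May not be | May stay on the ILI page |
| Nonserious, any onset | No route given | May stay on the ILI page |

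**3. Would another output catch the exposed cases?** Protocol 9.3.5 and SAP 6.6.1 do not depend on the AE page, but they stop at 14 days and cover test results or symptoms, not confirmed diagnoses. For the third row, where the ILI starts on Day 15 or later, no second output is specified. For the fourth row they help only if onset is early and tests or symptoms were recorded.

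**4. What could it amount to?** The conflict rests on no figure. For scale, Protocol Table 7 gives the chance of at least one event as 1 − (1 − p)^N. Its 0.01% row reproduces:

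- N = 18,100: 1 − 0.9999^18,100 = 0.836 (stated 0.84), with 18,100 × 0.0001 = 1.81 events expected.
- N = 23,100: 1 − 0.9999^23,100 = 0.901 (stated 0.90).

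If a share f of cases were missed, p becomes 0.0001 × (1 − f). The documents give no value for f, so these are assumptions:

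| f (assumed) | N = 18,100 | N = 23,100 |
|---|---|---|
| 0 | 0.84 | 0.90 |
| 10% | 0.80 | 0.88 |
| 25% | 0.74 | 0.82 |
| 50% | 0.60 | 0.69 |

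For example, with f = 25% and N = 18,100: 1 − (1 − 0.000075)^18,100 = 0.743. The table applies f to every case alike, although step 2 shows that some serious cases are returned. It shows sensitivity only and does not estimate loss.

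**The case against.** The strongest reply is that 8.4.8 is the more specific and the firmer instruction. It says must, and covers all AESIs, where the AE-page bar in 8.4.7 says should not and reaches only events potentially consistent with an efficacy endpoint definition. No visible endpoint definition mentions myocarditis or pericarditis. A site that reads 8.4.8 will record the case.

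Other safeguards add to this. Either NOTE condition turns the event into an SAE, and an investigator could readily find a myocarditis worse than expected. Protocol 10.2.3 treats an event of unknown cause as related for reporting purposes. Protocol 8.10.6 says that, in the 7 days after vaccination, symptoms overlapping with reactogenicity should not trigger an ILI visit unless the picture points more to ILI.

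Most of this stands and limits the point. It does not remove it. The safeguards turn on the investigator's judgment, and one who attributes the event to influenza may find that neither condition applies. The wording limit in 8.4.7 is not clear protection either, because the section itself counts pneumonia as a covered sequela.

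A reader might infer three stronger things that the documents do not support:

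- That every ILI-attributed case drops out of the count. It does not if the site follows 8.4.8, if a NOTE condition applies, or if the reviewer returns the event.
- That serious cases in the first days after vaccination are the ones lost, because 8.4.7 has no Day 15 start. Those cannot meet the primary endpoint and should be returned.
- That the fall from 0.84 to 0.74 or 0.60 is a predicted loss. The shares behind it are assumed.

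**Conclusion.** The passages conflict, and no precedence is stated. The exposed cases are nonserious ones, and serious ones tied to a primary-endpoint LCI with onset from Day 15, when they are regarded as ILI sequelae. These may be recorded on the ILI page only, and so be missed from the only count of confirmed AESIs that the SAP specifies, unless an 8.4.7 condition is applied or the site follows 8.4.8.

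How many cases this would touch cannot be derived from the documents. With about 1.8 events expected at a 0.01% rate and N = 18,100, even one matters, and that is as far as the arithmetic goes. The 0.01% rate is the lowest in Table 7, used here as an assumption and not as an estimate for qIRV. This is a reconciliation to make before the AESI summary is produced. It is not evidence that the safety data are unsound.

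**What to change.** **Protocol.** Reconcile the passages by stating in 8.4.7, 8.4.1(a) and 8.10.6.1 that the ILI carve-out does not apply to AESIs. A confirmed myocarditis or pericarditis is recorded as an AE or an SAE according to seriousness, as 8.4.8 already requires, in addition to its entry on the ILI page. Make this a separate sentence. It should not become a third condition in the 8.4.7 NOTE, because every event listed there is reported as an SAE, and a nonserious AESI would then be misclassified.

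**SAP 3.1.2.4.** State that the AESI variable is reconciled against ILI-page diagnoses, with each participant counted once.

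**Cost.** One sentence in each of three protocol sections and one in the SAP. The ILI-page diagnoses are already collected under 8.10.6.1, so no new data or procedure is needed, and the evaluation rules in 8.10.8 are untouched. The downside is a small amount of coding and de-duplication of those diagnoses, which neither document now describes.

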##### **8.4.8.1. Lack of Efficacy**

The investigator must report signs, symptoms, and/or clinical sequelae resulting from lack of efficacy. Lack of efficacy or failure of expected pharmacological action is reportable to Pfizer Safety **only if associated with an SAE**.

#### **8.4.9. Medical Device Deficiencies**

Medical devices being provided for use in this study are those listed in [Section 6.1.2](#). In order to fulfill regulatory reporting obligations worldwide, the unblinded site staff is responsible for the detection and documentation of events meeting the definitions of device deficiency that occur during the study with such devices.

The definition of a medical device deficiency can be found in [Section 10.8](#).

Note: AEs and/or SAEs that are associated with a medical device deficiency will follow the same processes as other AEs or SAEs, as outlined in [Sections 8.4.1](#) through [8.4.4](#) and [Section 10.2](#) of the protocol.

##### **8.4.9.1. Time Period for Detecting Medical Device Deficiencies**

Medical device deficiencies that result in an incident will be detected, documented, and reported during all periods of the study in which the medical device is used.

Importantly, reportable device deficiencies are not limited to problems with the device itself but also include incorrect or improper use of the device and even intentional misuse, etc.

If the unblinded site staff learns of any device deficiency at any time after a participant has been discharged from the study, and such deficiency is considered reasonably related to a medical device provided for the study, the unblinded site staff will promptly notify the sponsor.

The method of documenting medical device deficiencies is provided in [Section 10.8](#).

##### **8.4.9.2. Follow-Up of Medical Device Deficiencies**

Follow-up applies to all participants, including those who discontinue study intervention.

The unblinded site staff is responsible for ensuring that follow-up includes any supplemental investigations as indicated to elucidate the nature and/or causality of the deficiency.

New or updated information will be recorded on a follow-up form with all changes signed and dated by the unblinded site staff.

##### **8.4.9.3. Prompt Reporting of Device Deficiencies to the Sponsor**

When a device deficiency occurs:

1. The unblinded site staff notifies the sponsor by a contact method as detailed in the IPM within 1 business day of determining that the incident meets the protocol definition of a medical device deficiency.
2. The device deficiency must be recorded on the Medical Device Complaint form.

3. If an AE (either serious or nonserious) associated with the device deficiency occurs, then the AE must be entered into the AE section of the CRF.
4. If an SAE associated with the device deficiency is brought to the attention of the unblinded site staff, the unblinded site staff must immediately notify Pfizer Safety of the SAE (see [Section 8.4.1.1](#)). All relevant details related to the role of the device in the event must be included in the Vaccine SAE Reporting Form as outlined in [Sections 8.4.1.1](#) and [8.4.1.2](#).

The sponsor will be the contact for the receipt of device deficiency information.

#### **8.4.9.4. Regulatory Reporting Requirements for Device Deficiencies**

The unblinded site staff will promptly report all device deficiencies occurring with any medical device provided for use in the study in order for the sponsor to fulfill the legal responsibility to notify appropriate regulatory authorities and other entities about certain safety information relating to medical devices being used in clinical studies.

The unblinded site staff, or responsible person according to local requirements (eg, the head of the medical institution), will comply with the applicable local regulatory requirements relating to the reporting of device deficiencies to the IRB/EC.

#### **8.4.10. Vaccination Errors**

Vaccination errors may result from the administration or consumption of the study intervention by the wrong participant, or at the wrong time, or at the wrong dosage strength.

Vaccination errors are recorded and reported as follows:

Recorded on the Vaccination Error Page of the CRF	Recorded on the Adverse Event Page of the CRF	Reported on the Vaccine SAE Reporting Form to Pfizer Safety Within 24 Hours of Awareness
All (regardless of whether associated with an AE)	Any AE or SAE associated with the Vaccination error	Only if associated with an SAE

Vaccination errors include:

- Vaccination errors involving participant exposure to the study intervention;
- Potential vaccination errors or uses outside of what is foreseen in the protocol that do or do not involve the study participant;
- The administration of expired study intervention;

- The administration of an incorrect study intervention;
- The administration of an incorrect dosage;
- The administration of study intervention that has undergone temperature excursion from the specified storage range, unless it is determined by the sponsor that the study intervention under question is acceptable for use.

Such vaccination errors occurring to a study participant are to be captured on the vaccination error page of the CRF, which is a specific version of the AE page.

Whether or not the vaccination error is accompanied by an AE, as determined by the investigator, the vaccination error is recorded on the vaccination error page of the CRF and, if applicable, any associated AE(s), serious and nonserious, are recorded on the AE page of the CRF.

In the event of a vaccination dosing error, the sponsor should be notified within 24 hours.

Vaccination errors should be reported to Pfizer Safety within 24 hours on a Vaccine SAE Reporting Form **only when associated with an SAE**.

## 8.5. Pharmacokinetics

Pharmacokinetic parameters are not evaluated in this study.

## 8.6. Genetics

### 8.6.1. Specified Genetics

Some of the blood samples collected for CCI [REDACTED] may be used for CCI [REDACTED]. The CCI [REDACTED] [REDACTED]

CCl [REDACTED] See Section 10.4 for information regarding genetic research. Details on processes for collection and shipment of these samples will be provided separately.

## 8.7. Biomarkers

Biomarkers are not evaluated in this study.

## 8.8. Immunogenicity Assessments

Immunogenicity assessments are described in [Section 8.2.2](#).

8.9. CCI [REDACTED]

CCI [REDACTED]

Details will be specified in the SAP.

## 8.10. Study Procedures

### 8.10.1. Communication and Use of Technology

In a study of this nature that requires illness events to be reported outside of scheduled study visits, it is vital that communication between the study site and the participant is maintained to ensure that endpoint events are not missed. This study will employ various methods, tailored to the individual participant, to ensure that communication is maintained and study information can be transmitted securely. Using appropriate technology, such as a study application, a communication pathway between the participant and the study site staff will be established. The participant may be able to utilize his or her own devices to access this technology, or use a device provided by the sponsor. Traditional methods of telephone communication will also be available. The technology solution may facilitate the following:

- Contact with the investigator, including the ability of the participant to report whether or not the participant has experienced ILI symptoms and/or medically attended events for an ILI, eg, telephone consultation with a medical practitioner, doctor's visit, emergency room visit, or hospitalization (ILI e-diary; see [Section 8.10.6](#)).
- An alert in the event that the participant is hospitalized.
- Visit reminders.
- Messages of thanks and encouragement from the study team.
- Message to confirm that study participation and/or ILI surveillance has completed.
- A platform for recording local reactions and systemic events (reactogenicity e-diary; see [Section 8.3.4](#)).

The investigator or designee will review ILI e-diary data online at frequent intervals following vaccination to evaluate participant compliance and as part of the ongoing safety review. If a participant is not actively completing either the reactogenicity or ILI e-diary, the investigator or designee is required to contact the participant to ascertain why and also to obtain details of any missed events.

